8.5 Does this study only involve the use of existing/retrospective data/specimens?

Check yes or no.

No

8.6 Describe in detail the study design also known as the experimental flow. Include all study procedures a subject will go through, in order of sequence and timing, including frequency of visits, duration of visits, length of subject participation etc. Please Note this needs to be written for an educated person who is not an expert in the field, do not exceed 300 words:

This is also known as NIH Experimental Procedure section or Clinical Trial Procedure/Experimental Flow section. Do not just attach documents in response to this question you must do a study design summary for IRB Review.

The duration of each subject's participation will be ~4 months.

Visit 1 – Consent/Eligibility: Consent form signed; assessed for eligibility per inclusion/exclusion criteria; MMSE administered; BDI, PCS & FABQ administered; medical history, demographics, comorbidities, and medication use recorded; blood drawn for INR (in applicable subjects); pregnancy test (in applicable subjects). (~3.5 hrs)

Visit 2 – Baseline Outcomes Assessment: Study outcome measures (see Outcomes Assessment) administered to establish baseline levels. (~4 hrs)

Visit 3 - Sprint MicroLead (Electrode) Implant Procedure: Testing of muscle response with Sprint Test Needles; Implantation of percutaneous Sprint MicroLead. Subject given instructions on care of Lead exit site. Skin checked, subject queried for medication usage. Randomization to treatment group. Subset of study outcome measures (questionnaires only) administered. (~2.5 hrs)

Visit 4 - 48-72 hour Post-Implant Safety Check: Check the Lead exit site within 48-72 hours of the Implant procedure; dressing changed. (~1 hr)

Visit 5 - Start of Stimulation: Collection of parameter data; programming of external stimulator (Sprint Stimulator). Subject given instructions on use of System and care of Lead exit site. Skin checked, dressing changed, subject queried for medication usage and adverse events. Subset of study outcome measures (BPI-SF only) administered. (~2 hrs)

Phone Call #1 – One week after starting stimulation, subject queried on condition of Lead exit site, pain, adverse events. (30 min)

Phone Call #2 – Two weeks after starting stimulation, subject queried on condition of Lead exit site, pain, adverse events. (30 min)

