Visit 6 - EOT Outcomes Assessment & Explant Procedure: Study outcome measures administered (4 weeks post-Implant). PGIC administered. Skin checked, subject queried for medication usage and adverse events. Lead Removed. X-rays performed (may be done as separate clinical visit). (~4.5 hrs)

Phone Call #3 - 1 week Post-Explant Safety Check: Subject queried on condition of Lead exit site. (15 min)

Visit 7 - 8-wk Outcomes Assessment: Subset of study outcome measures

(questionnaires only) administered (8 weeks post-Implant (4 weeks post-EOT)).
Subject queried for medication usage. (~1 hr)

Visit 8 - 12-wk Outcomes Assessment: Subset of study outcome measures
(questionnaires only) administered (12 weeks post-Implant (8 weeks post-EOT)).
Subject queried for medication usage. (~1 hr)

Visit 9 - 16-wk Outcomes Assessment: Study outcome measures administered (16
weeks post-Implant (12 weeks post-EOT)). Subject queried for medication usage.
(~4 hrs)

Provision for lead replacement: If, in the judgement of the Investigator, the Sprint
MicroLead becomes significantly displaced or fully dislodged, it is possible that the
Investigator may elect to place another lead which would require an unscheduled
visit and additional 48-72 hour safety check. Other visits may be repeated as
appropriate.

Unscheduled Visits are conducted if/as needed.

8.7 Please attach study design/subject visit schedule here:

Name	Description
PNS Dose for HSP Visit Schedule Table (06-14-2017) History	

*If you have an
electronic schedule of study visits
and/or procedures please attach
here.*

View: 09-00 Inclusion/Exclusion Criteria

9.0 Inclusion/Exclusion Criteria:

9.1 What are the inclusion criteria? Put this information in bullet form:

- shoulder pain localized to the glenohumeral joint, subacromial area or deltoid insertion associated with: a) rest; b) passive abduction or external rotation range of motion (ROM); c) active abduction ROM; or, d) manual palpation;
- shoulder pain onset or worsening after the most recent stroke;
- weakness of shoulder abductors ($\leq 4/5$ on MRC if isolated movement is present);
- ≥ 21 -yrs old; < 90 -yrs old;
- time of stroke ≥ 3 -mo;
- duration of HSP ≥ 3 -mo;
- HSP with moderate to severe pain (BPI SF-3 ≥ 4);
- cognitive and communication ability to fulfill study requirements (cognitive ability based upon a score of ≥ 24 on the Mini Mental Status Exam (MMSE));
- availability of reliable adult who can assist with study procedures if necessary;

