A Lead fragment could result in the formation of a granuloma or infection. Although the occurrence of a fragment-related infection or granuloma is uncommon an infection may require removal of the Lead fragment and/or treatment with antibiotics. Investigators at the Cleveland FES Center and Case Western Reserve University have over 30 years of experience with dozens of research participants and hundreds of implanted leads like those used in this study. Infections and granulomas of leads or lead fragments have been uncommon, which is attributed to the materials and procedures that have been developed as well as the extensive experience of the Investigators..

5) Risks associated with lead fragment removal

It is possible that a Lead fragment or fragments may be retained in the body following removal of the Sprint MicroLead. If the Investigator determines that a lead fragment has been retained, the Investigator will instruct the subject and his/her caregiver to carefully inspect the Sprint MicroLead exit site and the surrounding skin in the weeks subsequent to Lead removal. Subjects will be instructed to contact the Investigator if there are any signs of pain, redness, swelling, discharge, or the appearance of a pimple-like mass (skin abscess). Such signs indicate that the fragment has migrated to the skin surface. At that time, if clinically warranted, the fragment may be removed via an outpatient procedure which involves lancing the abscess and removing the fragment and application of a topical antibiotic.

The risks associated with the Lead fragment removal procedure include discomfort during the procedure and skin irritation or infection in the area of the retained fragment. These risks are rare. The risk of infection is

mitigated by instructing the subject and/or his caregiver to carefully monitor the site and immediately report any signs of infection.

6) Risk of Lead Replacement due to Lead Migration or Lead Becoming Dislodged

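### Section 8.6 lists no general adverse-event query after end of treatment, so events outside the shoulder in the last 12 of 16 post-implant weeks rely on spontaneous report

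*Protocol*

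**What the plan says.** Section 8.6 (study design and experimental flow) goes through the contacts in order. The safety questions after implant are these.

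- Visit 5, start of stimulation: "Skin checked, dressing changed, subject queried for medication usage and adverse events".
- Phone Call #1: "One week after starting stimulation, subject queried on condition of Lead exit site, pain, adverse events".
- Phone Call #2: "Two weeks after starting stimulation, subject queried on condition of Lead exit site, pain, adverse events".
- Visit 6, end of treatment (EOT) and explant: "Skin checked, subject queried for medication usage and adverse events. Lead Removed".
- Phone Call #3, one week after explant: "Subject queried on condition of Lead exit site. (15 min".
- Visits 7 and 8: questionnaires and a medication query.
- Visit 9: all outcome measures, and again "weeks post-Implant (12 weeks post-EOT)). Subject queried for medication usage".

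Elsewhere, section 10.1 says the shoulder is inspected at every visit. Section 10.5, item 5, deals with retained lead fragments. Subjects found to have one, and their caregivers, are told to "carefully inspect the Sprint MicroLead exit site and the surrounding skin in the weeks subsequent to Lead removal", and to contact the investigator if signs appear. Section 18.01 lists subject interview or contact, physical examination, symptoms and interim adverse-event assessment as safety data, with at least quarterly review of collected events. It does not say at which visits events are elicited.

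**The concern.** The wording at Visits 5 and 6 pairs medication use with adverse events. At Visits 7, 8 and 9 the same sentence keeps the medication half and loses the other. Staff working from 8.6 would ask about harms for four weeks and then stop, although follow-up runs for another twelve and the protocol itself foresees harms arising after the lead is out.

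What is at stake is the completeness of the harm record. Asking directly generally yields more events than waiting for subjects to volunteer them. If solicitation stops at EOT, a fall in event counts afterwards could reflect either fewer events or less asking, and the two periods cannot be compared fairly. The events most exposed are those no other scheduled procedure would detect: a systemic illness, a hospital admission, a problem away from the shoulder, or something that arose and resolved between visits.

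**Working it through.** There is no test or sample-size figure to reproduce. The check is a tabulation of contacts plus arithmetic on the stated visit times.

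**Inputs.** Stimulation starts after one week of lead stabilisation (8.4). Visit 6 is at week 4 post-implant, and Visits 7, 8 and 9 are at weeks 8, 12 and 16 (8.6). Phone Calls #1 and #2 fall one and two weeks after stimulation starts, at about weeks 2 and 3. Phone Call #3 is one week after explant, at about week 5.

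| Contact | Approx. week | General adverse-event query in 8.6 | Other safety question or check in 8.6 |
|---|---|---|---|
| Visit 4 | 48-72 h | no | exit site |
| Visit 5 | 1 | yes | skin, medication |
| Call #1 | 2 | yes | exit site, pain |
| Call #2 | 3 | yes | exit site, pain |
| Visit 6 | 4 | yes | skin, medication, x-ray |
| Call #3 | 5 | no | exit site |
| Visit 7 | 8 | no | medication |
| Visit 8 | 12 | no | medication |
| Visit 9 | 16 | no | medication |

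**The plan's own figure.** EOT to last visit is 16 - 4 = 12 weeks, which matches the 12 weeks of follow-up in 8.4 and the timing given for Visit 9.

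**Size of the gap.** Weeks with no general adverse-event query: 12 of 16, and 12/16 = 75%. Contacts naming such a query: four up to and including Visit 6, and 0 of 4 afterwards. Counting Phone Call #3 as a partial safety question, the stretch in which 8.6 lists no safety question beyond medication use is 16 - 5 = 11 weeks.

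**What other provisions cover in weeks 4-16.**

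- *Exit site and skin:* Phone Call #3, and the per-visit inspection in 10.1. These are not fully aligned, because 8.6 lists a skin check at Visits 3, 5 and 6 but not at Visits 7-9.
- *Retained fragments:* x-ray after explant identifies who has one, and those subjects are told what to watch for. This is targeted, but it remains self-report.
- *Pain:* BPI and SF-36 at weeks 8, 12 and 16, so worsening pain would be seen as an outcome even if not logged as an adverse event.
- *Systemic, non-shoulder or resolved events:* no direct question. The medication query might reveal some indirectly, through a new antibiotic for example.

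**After the change.** With queries at about weeks 5, 8, 12 and 16 following the one at week 4, the intervals are 1, 3, 4 and 4 weeks. The longest is 4 weeks, and no part of follow-up is left unasked.

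**The case against.** The best counter-argument is that 8.6 is a lay summary with a requested limit of 300 words, so silence there proves little. Visit 4, whose sole purpose is safety, also names no adverse-event query. The visit schedule (8.7), the adverse-event and survey-visit forms (14.7) and the monitoring plan (18.01) are attached but not shown, and any of them may contain the question. Section 18.01 lists interview and symptoms as safety data without confining them to the treatment phase, and the last inclusion criterion in 9.1 requires subjects willing to report conditions throughout the four months.

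Part of this stands: an unseen attachment may already close the gap. The rest is weaker. The 8.6 prompt asks for all study procedures, and 14.3 cites 8.6 as one of the places where the data collected are described in detail. The answer already runs to about 435 words, so the limit did not force out the missing phrase. Visit 4 is followed within days by a general query at Visit 5 that can pick up what it missed, whereas nothing follows Visit 6. A quarterly review can only consider events that were collected.

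A reader might infer more than the text supports, in three ways.

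- *That the harms expected after lead removal go unsolicited.* They do not, entirely. Phone Call #3 is a solicited safety check, the shoulder is to be inspected at each visit, and the foreseen fragment harms (redness, swelling, discharge, abscess) are local and largely visible.
- *That earlier lead breakages predict missed late harms.* Section 21.21 says none of the breaks in the earlier randomised trial resulted in an adverse event.
- *That the comparison between dose groups is biased.* The same schedule applies to all three groups, stimulation has ended by Visit 6, and the document identifies no late dose-related harm.

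**Conclusion.** The point holds in a limited form. As 8.6 is written, general adverse-event queries stop at EOT, and for 12 of 16 post-implant weeks (75%) systemic, non-shoulder or already resolved events depend on spontaneous report. Late harms may be under-counted, and event counts from the treatment and follow-up periods are not on the same footing. The documents give no basis for estimating how many events would be missed. The effect is on completeness and is the same in every arm. It does not touch the primary outcome.

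This rests on two assumptions: that sites follow 8.6 as worded, and that the attached schedule and forms do not already carry the query. If they do, what remains is a mismatch for 8.6 to correct. Either way it is a cheap improvement worth making, not a flaw that threatens the trial.

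**What to change.** In 8.6, use at Visits 7, 8 and 9 the wording already used at Visits 5 and 6: "subject queried for medication usage and adverse events". Add adverse events to the questions at Phone Call #3. Check that the attached visit schedule agrees, and amend it only if it does not. While doing so, reconcile the per-visit inspection in 10.1 with the skin checks listed in 8.6.

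The cost is a few minutes per contact, using the adverse-event form already listed in 14.7, at four contacts that are already scheduled. No visit, instrument or clinical rule changes.

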9.3 How will subject eligibility be determined and by whom?*Please describe in detail.*

Subject eligibility will be initially assessed by the study coordinator and will be confirmed and reviewed by the Investigator. Eligibility will be determined from:

- review of medical history available in the chart;
- completion of the Brief Pain Inventory Short Form (to confirm baseline degree of pain of ≥ 4);
- bloodwork (to confirm suitable coagulation levels in patients on anticoagulants) or pregnancy urine or serum test in applicable female subjects;
- physical examination of shoulder.

9.4 Will you exclude women and minorities, or persons under 21 from enrollment?*Check yes or no.*

Yes

9.5 If yes, which groups are you excluding? Provide justification for your decision.*List groups to be excluded then provide justification.*

Pregnant women: Pregnant women will be excluded since the effect of electrical stimulation on the fetus is not known.

Persons under 21: Children are excluded based on scientific considerations as they represent a fundamentally different population with chronic post-stroke shoulder pain etiologies and substantially different from the adult population. Individuals that are at least 21 years of age possess additional maturity beyond those that are 18. The study involves the use of an external stimulator and requires the maintenance of a percutaneous exit site. As such, we believe that this additional level of maturity is a valid reason to extend the minimum age of enrollment to 21.

9.6 Attach Documents:*If you are unable to fit your answers in the text boxes provided please attach as a word document.*

Name	Description
There are no items to display	

View: 10-00 Risk/Benefits

10.0 Assessment of Risk I:**10.1 Identify and distinguish between those procedures that are standard versus those that are experimental. Include the frequency and duration of each activity and the total length of subject participation:***Please distinguish between those procedures that are standard versus those that are experimental. Describe in detail all experimental procedures.*

- Physical Exam and Range of Motion of shoulder (standard): A physical exam and range of motion assessment is standard for patients with shoulder pain and will be done at Visit 1. The shoulder will be physically inspected during each visit.
- Collection of bloodwork (standard): The blood test (INR score) is standard for patients taking anticoagulants. This test will be collected in applicable subjects at Visit 1. A standard pregnancy test will also be administered in applicable subjects and can either be urine or serum pregnancy test.
- EMG needle electrode testing (experimental): EMG needles are commonly used to evaluate muscle physiology and strength of muscle contractions. In this study, however, EMG needle (Sprint Test Needle) testing will be used to deliver test stimulation during the lead implant procedure.
- Placement of Percutaneous Fine Wire Intramuscular Lead (experimental): The placement of the lead during the lead implant procedure and the use of stimulation during the treatment phase are experimental. Local anesthetic will be used.
- X-rays (standard): One 2-view (AP/Lateral and Scapular Y) shoulder x-ray will be conducted following the removal (explant) of the electrode lead, to determine and document the presence of any retained fragments.
- Collection of surveys and questionnaires - BPI, SF-36 (standard): These surveys are used for research, but are commonly used in pain patients. These surveys will be collected as defined elsewhere in this protocol for Outcomes Assessments Visits; the BPI additionally is collected at the Start of Stimulation Visit. The Mini Mental Status Exam (MMSE, also standard) will be collected at Visit 1. The BDI and PCS (also standard) are used for research, but are commonly used in pain patients. They will be collected at Visit 1. The FABQ (experimental) will be collected at Visit 1. The PGIC (experimental) will be collected at Visit 6.
- Fugl-Meyer Motor Assessment (upper limb): The FMA (standard) will be used as defined elsewhere in this protocol for Outcomes Assessments Visits.
- Other outcomes measures (experimental): Isometric voluntary abduction shoulder torque (IVAST), shoulder kinematic analysis, and measures of central sensitization (mechanical pain thresholds for hyperalgesia, pinprick pain thresholds for hyperalgesia, temporal summation of repetitive pin-prick stimuli) are used for research but some also are used in clinical practice as well. They will be used as defined elsewhere in this protocol for Outcomes Assessments Visits. Optional measures include tactile/touch, vibration and thermal/thermal pain detection thresholds, temporal summation of repetitive thermal stimuli, and Conditioned Pain

Modulation (CPM). They also are used for research but some also are used in clinical practice as well.

10.2 Describe any therapeutic alternatives to the research that may exist. How are they different from those procedures that subjects would normally undergo?

Describe any therapeutic alternatives. Can subjects receive this drug or device outside of a research study?

Numerous interventions exist for the treatment of shoulder pain following stroke. This is due to the large number of possible etiologies, the diversity of clinicians that treat stroke patients, and the lack of consensus regarding a standard of care. None of the following interventions have been shown to reduce pain reliably in randomized controlled trials.

Slings and other supports: Arm slings and other mechanical supports, such as wheelchair trays, are often used to support the forearm and distribute its weight to one or both shoulders in an effort to prevent or reduce subluxation. Although slings may reduce subluxation, they often fail to reduce shoulder pain as subluxation recurs once they are removed and may slow rehabilitation by reducing arm mobility.

Strapping: Strapping is the application of non-stretch tape to the affected limb to support the glenohumeral joint while allowing free movement of the arm. In a randomized controlled study of 33 patients, those who received strapping reported reduced average pain compared to those who received no therapy (inactive control group). However, strapping fails to produce a significant benefit compared to active control groups, who received either sham strapping or standard physiotherapy without strapping. In addition, the tapes must be replaced at least every three days, and skin irritation is common.

Local Injection Techniques: Corticosteroid injections address pain by treating inflammation. Approximately 50% of clinicians who treat patients with poststroke shoulder pain believe that steroid injections are effective. However, there are only two randomized controlled trials of corticosteroid injections for the treatment of post-stroke shoulder pain and they have mixed results. A recent trial of subacromial injections reported significant benefit over placebo. However, an earlier placebo controlled trial of intra-articular injections showed no benefit. Post-stroke shoulder pain has a variety of possible etiologies and does not always arise from inflammation, explaining why steroid injections do not consistently outperform placebo in stroke patients. In addition to uncertain efficacy, repeat corticosteroid injections are associated with frequent adverse events, making them a poor treatment option.

Botulinum toxin causes local paresis of muscles by blocking cholinergic transmission at the neuromuscular junction. It has been widely used to treat spasticity and some data suggest that it may also help to relieve pain. Six of nine patients in a small uncontrolled study receiving an injection of botulinum toxin to the affected limb reported pain reduction. However, the effect of botulinum toxin is known to diminish after 3-4 months, making repeated injections necessary. Little data exist regarding the repeated use of botulinum toxin for shoulder pain relief.

Oral analgesic medications: The use of opioid and nonopioid analgesics, including nonsteroidal anti-inflammatory drugs (NSAIDs) to manage shoulder pain is common practice. Unfortunately, extended use of opioids can lead to dependence and side effects such as headache, skin rash, dizziness, and gastrointestinal symptoms. Though NSAIDs may reduce shoulder pain in the general population, their efficacy has not been demonstrated in the stroke population.

Therapeutic exercises: Therapeutic exercises under the supervision of a trained professional are generally considered to be an important part of poststroke rehabilitation. Although they prevent immobility and improve the range of motion (ROM) of the hemiplegic arm, studies have found that some exercises, such as the use of an overhead pulley, can cause soft tissue damage and thereby worsen shoulder pain. In fact, exercises are generally associated with a worsening of pain or no change, rather than an improvement. In a study investigating static positional stretches, the treatment group showed increasing levels of pain.

Acupuncture/Electroacupuncture: Acupuncture has been used for centuries to treat various types of pain and is believed to improve cutaneous and

muscle blood flow and to increase pain thresholds. Electroacupuncture, a therapy in which traditional acupuncture needles are used in conjunction with electrical stimulation, has been evaluated as a therapy for shoulder pain in post-stroke subjects in a randomized study comparing electroacupuncture plus occupational/physical therapy to therapy alone. Although statistically significant improvements in pain reported via a Visual Analog Scale were observed in the treatment group, the study did not follow the group beyond the conclusion of the treatment. Thus it is not clear how often the therapy must be reapplied. In addition, electroacupuncture requires repeated clinic visits (at least 3 visits per week for 1 month). Traditional acupuncture has also been evaluated as a treatment for shoulder pain; however subjects in these studies had non-stroke shoulder pain etiologies.

Surface electrical stimulation: Surface electrical stimulation uses skin surface electrodes applied to the shoulder to deliver stimulation from an external stimulator. Baker and Parker published the first results from a randomized controlled trial of surface electrical stimulation for the treatment of poststroke shoulder pain. The authors found a treatment effect for subluxation but inconclusive results regarding pain relief. The investigators of a later study hoped to obtain more conclusive results than Baker and Parker by enrolling a larger population of 120 and following the subjects for two years. Pain was noted as present or absent at rest during passive motion and during active motion. Subjects were also asked to rate their pain using a visual analogue scale (VAS). For a subject to be classified as having no pain, all four variables had to be negative. A significantly higher proportion of subjects receiving electrical stimulation had no pain at 3, 6, 12, and 24 months compared to the control group (80.7% vs. 55.1%, $p < 0.01$). The treatment subjects also showed a greater reduction in subluxation and a significant improvement in the recovery of arm motion.

The results of four additional studies investigating surface electrical stimulation are summarized in a Cochrane review. Although the authors found a significant improvement in pain-free range of motion (ROM) in the treatment groups, the data did not support a significant reduction in pain intensity or incidence. The authors concluded that larger randomized controlled studies would be necessary to fully examine the effects of electrical stimulation in the post-stroke shoulder pain population. Another literature review including six trials found that electrical stimulation paired with conventional therapy is not superior to conventional therapy alone for pain prevention. However, they noted that this may be due to the indirect way in which most studies measured pain (as "pain-free range of shoulder external rotation"). When pain was measured directly, using a VAS, electrical stimulation was found to be more effective in preventing pain than conventional therapy.

The results regarding the efficacy of surface electrical stimulation as a treatment for post-stroke shoulder pain have been promising, leading to its recommendation by several recently published guidelines. In addition, a literature review proposed that surface electrical stimulation combined with gentle clinician guided exercises should be considered the "best practice" for acute stroke survivors. However, several authors have noted that even with further evidence of the efficacy of surface electrical stimulation, it is unlikely that it will ever be the standard of care due to the discomfort caused by stimulation of cutaneous pain receptors, the potential for skin irritation under multiple surface electrodes, the need for skilled personnel to place the surface electrodes on a daily basis, and muscle fatigue that commonly occurs due to the high frequency of stimulation. Baker and Parker noted that either an implantable or a percutaneous system would have to be developed before electrical stimulation could become the preferred treatment. For these reasons, researchers have turned their attention to the use of intramuscular electrical stimulation.

bion® microstimulator (investigational): Due to the effectiveness of electrical stimulation but the difficulties associated with surface electrical stimulation, researchers have begun to investigate direct muscle and nerve stimulation. The bion® microstimulator used by Bioness, Inc. (Valencia, CA), is currently being investigated for the treatment of post-stroke shoulder pain and subluxation. Although the bion has technical advantages, including its small size and self-contained electrode, it also suffers from considerable disadvantages. First, the device does not utilize a trial stage to evaluate whether a candidate is likely to experience pain relief from long term use

prior to implantation. Second, implantation of the bion requires fluoroscopy and precise placement in close proximity to the deep axillary nerve trunk. Third, the device must be recharged daily using a large, stationary charging apparatus, to which the patient must be tethered during the recharging session. In addition, the bion's extraction requires open surgery. Finally, the bion requires precise placement due to its bipolar configuration, as the stimulus current density (and efficiency of nerve recruitment) drops off rapidly with distance from the target nerve. Even a small migration of the bion could significantly diminish its effectiveness. Data regarding the safe and effective use of the bion for post-stroke shoulder pain have not yet been published.

- 10.3 What are the outcome variables and how will they be analyzed? What are the statistical and analytical methods that will be used? Note this section can be copied from the NIH Grant Application or from the Statistical and Analytical Methods section of the industry trial protocol.**
See 8.4 and attachment below.

Define outcomes and describe data analysis, please include a power calculation.

- 10.4 If the above requested information does not fit in the text box please attach a word document here:**

If the requested information does not fit in the text box please attach a word document.

Name	Description
Outcomes Measures and Data Analysis History	

View: 10-01 Risk/Benefits

10.1 Assessment of Risk II:

- 10.5 List and quantitate the risks involved for each experimental procedure in bullet form. Identify risks as common (greater than 10%) uncommon (greater than 1% up to and including 10 %) rare (1% or less). This must match the risks listed in the Consent Form:**
1) Risks associated with needle insertion for Sprint MicroLead placement

Select all that apply.

There are minor risks associated with inserting a Lead through the skin with a needle. These risks are similar to the risks of any needle injection including the possibilities of puncturing a blood vessel, irritating a nerve, and temporary bruising or pain at the insertion site. The risks of puncturing a blood vessel and irritating a nerve are uncommon, but the risks of temporary bruising and pain at the insertion site are common.

Some participants may experience a vasovagal ("fainting") response due to the discomfort or anxiety associated with of the procedure, especially among those with prior history of "fainting." This risk is rare and may be associated with symptoms of lightheadedness, dizziness and or diaphoresis with concomitant reduction in blood pressure and heart rate. For those with prior history of "fainting" the procedure will be performed with the subject in the lateral decubitus position.

To minimize the risks associated with percutaneously placing fine wire leads, only appropriately trained physician investigators will perform the procedure. In addition, the risk of excessive bleeding will be reduced by excluding candidates who are taking warfarin with an INR > 3.0 and by placing manual pressure on the implantation site until hemostasis is achieved. Finally, the risk of discomfort during the procedure will be reduced by the use of an appropriate amount of local anesthetic.

It is possible that, in some cases, multiple attempts may be required to achieve appropriate placement of the Lead during the procedure. Each additional attempt at Lead placement carries the same risks as the initial attempt described in this section.

- 2) Risk of skin irritation, infection, or inflammation at the Sprint MicroLead exit site

There are risks of leaving a Sprint MicroLead in place for 4 weeks, including skin irritation, infection, and granuloma formation (mild tissue inflammation) at the Lead exit site. Symptoms include redness, swelling, or pain. The risk of skin irritation is common while the risks of infection and granuloma formation are rare.

These risks will be minimized by using sterile Leads and thoroughly

insertion. The insertion site will be covered with a dressing to keep it clean and dry, and the subjects and their caregivers will be instructed to inspect the site for signs of infection or irritation regularly and to inform the Investigator if they occur. If infection or skin irritation occurs, the Investigator will administer an antibiotic and/or remove the Lead. Infections are rare and typically resolve after Lead removal and antibiotic treatment.

